10.4 Pregnancy

If any pregnancies are reported during the study, as collected from the Pregnancy Report eCRF, these will be listed, along with the information from the Pregnancy History and Pregnancy Outcome Log eCRFs.

10.5 HIV Testing

If any positive Rapid HIV test results are reported, the number and proportion of participants with positive results as collected in the HIV Test Results eCRF will be summarized in a table by arm. For any positive results, a listing from the HIV Confirmatory Test Results eCRF will be presented.

11. EXPLORATORY ANALYSES

In this section, we describe some analyses related to exploratory endpoints for Adherence, and Acceptability that are considered of special interest.

11.1 Residual TFV levels in used rings

Residual TFV levels in returned IVRs will be reported. Tables with summary statistics appropriate for continuous measurements will be presented, by arm. Box plots and histograms for the residual TFV levels, by arm, will be produced.

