### **3.3 Exploratory Objectives**

#### **Adherence**

- To evaluate markers of ring use for the TFV IVR

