**Table 2: Study Regimen**

Group	N	Ring Description
A	32	TFV IVR containing 1.4 g TFV
B	16	Matching Placebo IVR

Each participant will receive either an TFV IVR containing 1.4 g TFV or a matching placebo IVR. Participants will be randomized in a 2:1 ratio. Participants will not be told their group assignment. The IVR is inserted once and used continuously for approximately 91 days. The IVR will be removed by the participant (or clinician/designee, if necessary) at the product use end visit (PUEV/Early Termination Visit). Participants will be followed for approximately 1 day following final IVR removal.

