#### 6.3.1 1.4 g TFV IVR

The 1.4 g TFV IVR is comprised of a drug-loaded hydrophilic polyether urethane (HPU) tube (white segment) that is sealed and joined together (transparent joint) to form the shape of a ring. This is a reservoir IVR using a water-absorbable polyurethane as a rate controlling membrane capable of delivering approximately 10 mg/day TFV for 90 days. The TFV IVR has a 0.7 mm wall thickness, 5.5 mm outer cross-sectional diameter and 55 mm outer diameter.

The TFV IVRs should be stored in the site pharmacy at 20°C to 25°C (68°F to 77°F), with allowable excursions between 15°C to 30°C (59°F to 86°F).

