### **6.3.2 Matching Placebo IVR**

The matching Placebo IVR has a similar appearance and dimensions to the TFV IVR. The composition of the matching Placebo IVR is also similar to the TFV IVR except that modified starch, which is non-eluting from the reservoir, is used to replace the TFV to provide a similar white filled tube appearance.

The matching Placebo IVRs should be stored in the site pharmacy at 20°C to 25°C (68°F to 77°F), with allowable excursions between 15°C to 30°C (59°F to 86°F).

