11.2 Total TFV released

The amount of TFV released for each ring will be estimated by subtracting the residual level measures from average TFV load level of the corresponding manufacturing batch. Tables with summary statistics, by arm, will be produced and box plots will be used to compare the distribution of the total TFV released.

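### SAP 11.1 and 11.2 set residual and released TFV out by arm, which shows only ring assignment, and no stated analysis relates any drug marker to ring use

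*SAP*

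**What the plan says.** The exploratory adherence objective in Protocol 3.3 reads "To evaluate markers of ring use for the TFV IVR". Protocol 4.4 lists its endpoints: plasma and CVF TFV, residual drug in returned rings, and biomarkers of ring use.

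SAP 11.1 reports residual TFV with summary tables and states: "Box plots and histograms for the residual TFV levels, by arm, will be produced". SAP 11.2 estimates released TFV by "subtracting the residual level measures from average TFV load level of the corresponding manufacturing batch", and continues: "Tables with summary statistics, by arm, will be produced and box plots will be used to compare the distribution of the total TFV released".

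Protocol Table 2 describes the active ring as "TFV IVR containing 1.4 g TFV". Protocol 6.3.2 says of the placebo ring that "modified starch, which is non-eluting from the reservoir, is used to replace the TFV".

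Ring-use data are handled elsewhere. SAP 9.1 combines self-reported outages with clinician-recorded ones from the termination, discontinuation, product-hold and ring insertion/removal forms. It summarizes the cumulative time the ring was out. It does not mention drug levels, and SAP 11.1 and 11.2 do not mention outages. SAP 8.1 summarizes plasma and CVF TFV over time, again without reference to ring use, though it does confine the detection proportion to the active arm.

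**The concern.** A marker of use is evaluated by relating it to use. Comparing TFV content between a ring loaded with TFV and one without it gives a result known before any ring is returned. The informative variation lies among TFV-arm participants, between those who kept the ring in throughout and those who did not, and no stated analysis looks at it.

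Protocol 2.4.3 says this is the first human study of the ring over its full 90 days. If the analysis stays as written, the reports will give the distribution of residual drug but will not say whether low release goes with time out of place. A later trial wanting an objective adherence measure would need that.

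**Working it through.** The plan states no figure for this analysis, so there is none to reproduce. The steps below use the documents' own load, release and adherence figures.

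**1. What the by-arm contrast can show.** Released = batch load − residual. For placebo, load = 0 and residual = 0, so released = 0 − 0 = 0 for every ring. The contrast carries no information on use.

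**2. Where the variation lies.** Protocol 6.3.1 describes the TFV ring as "capable of delivering approximately 10 mg/day TFV for 90 days". At 10 mg/day for 91 days, released = 10 × 91 = 910 mg and residual = 1,400 − 910 = 490 mg. Assuming release stops while the ring is out:
- 7 days out: 10 × 7 = 70 mg less, or 70/910 = 7.7% of expected release.
- 28 days out: 10 × 28 = 280 mg less, or 280/910 = 30.8%.

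**3. Could the marker detect this?** The documents give no between-woman SD for release over 90 days. As an illustration, take the animal means and SDs for time-averaged release in Protocol 2.3.2 and assume a ring out 20% of the time loses 20% of its release. Shift in SD units = 0.20 × mean / SD.

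| Species | Mean ± SD (mg/day) | CV | Shift |
|---|---|---|---|
| Sheep | 17.0 ± 1.1 | 6.5% | 3.4/1.1 = 3.1 SD |
| Rabbit (ring segments) | 3.7 ± 0.7 | 19% | 0.74/0.7 = 1.1 SD |
| Macaque | 13.6 ± 7.6 | 56% | 2.72/7.6 = 0.4 SD |

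The sheep figure is the optimistic end. Sheep rings held about 1.6 g and released 17.0 × 90 = 1,530 mg, about 96% of the load, so a ceiling may have compressed the spread. Nor does that rate carry over to this ring: 17.0 × 91 = 1,547 mg exceeds the 1,400 mg load, and the ring would be empty at 1,400/17.0 = 82 days. With that cap, 18 days out gives 73 × 17.0 = 1,241 mg against 1,400 mg. The difference of 159 mg is 159/91 = 1.75 mg/day, or 1.75/1.1 = 1.6 SD.

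**4. Precision of a within-arm analysis.** Assume all 32 TFV rings are returned and use the Fisher z approximation for a Pearson correlation. This is only a guide for Spearman, and less reliable with many ties.
- Two-sided 5% threshold: |r| = tanh(1.96/√29) = 0.35.
- 80% power: |r| = tanh((1.96 + 0.84)/√29) = 0.48.
- An observed r of 0.5 has a 95% CI of about 0.18 to 0.72.

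**5. How many would have an outage.** Protocol 10.4.2 illustrates adherence at 75%. Applied to the TFV arm, 0.25 × 32 = 8 with an outage and 24 without. With 80% power at two-sided 5%, the detectable difference is (1.96 + 0.84) × √(1/8 + 1/24) = 1.14 SD. The rabbit shift is close to that limit and the macaque shift is well below it.

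**The case against.** A reader might infer that the objective gets no answer, or that the trial would show only that drug rings contain drug. The documents do not support that. The listed endpoint is the residual drug level itself, and SAP 11.1 reports it. The TFV-arm half of each display can be set against the 1.4 g load and the nominal release, and unusually low release would be visible. SAP 8.1 reports plasma and CVF TFV at each collection time. SAP 11 says it covers only some exploratory analyses, so its silence does not rule out further work.

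The placebo display is also harmless. It is descriptive, carries no test and biases no TFV-arm figure. In SAP 11.2 the arm split is attached to the tables, while the box-plot clause, "box plots will be used to compare the distribution of the total TFV released", does not name the groups compared. That leaves room for a sensible reading of 11.2, but not of 11.1, where the plots are explicitly by arm.

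A reader might also infer from the sheep data that the marker discriminates well. That takes the tightest of three species at a rate this ring could not sustain for 91 days.

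Finally, the proposed reference is partly self-report, the measure an objective marker is meant to improve on, and the estimate may rest on a few participants with many ties at zero days out. This stands. It limits what the analysis can prove, but does not favor leaving the marker unrelated to use.

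**Conclusion.** The concern holds in a limited form. The between-arm layout in SAP 11.1 and 11.2 shows assignment only, and no stated analysis in either document relates residual, released, plasma or CVF TFV to ring use. The objective is answered descriptively and no further.

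How well the marker would work is unknown: a 20% fall in release could be anywhere from 0.4 to 3.1 SD on the animal data, assuming spread in women resembles one of those species and loss is proportional to time out. With up to 32 returned rings and perhaps 8 participants with an outage, the added analysis would give an estimate with a wide interval. The consequence is minor because the objective is exploratory and no primary or secondary result is affected.

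**What to change.** 1. Restrict SAP 11.1 and 11.2 to the TFV arm.
2. For each returned TFV ring, derive days in place from the SAP 9.1 outage, hold and discontinuation data. Match days to the individual ring, since Protocol 6.4.2 and 6.4.4 allow a replacement to be dispensed.
3. Plot TFV released against days in place, with a Spearman correlation and 95% CI, and summarize release by any versus no recorded outage.
4. Do the same for CVF and plasma TFV at matching visits. Protocol 2.4.3 reports that plasma TFV fell below quantification within 24 hours of removal in an earlier ring study, so plasma is best read against ring presence or outages close to the visit.
5. State that this is estimation only, that the reference is partly self-report, and how many rings and participants with an outage contribute.

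The cost is SAP wording, one derived variable (SAP 9.1 summarizes time out, not days in place per ring) and a few displays. No new data are collected.

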11.2 Total TFV released

The amount of TFV released for each ring will be estimated by subtracting the residual level measures from average TFV load level of the corresponding manufacturing batch. Tables with summary statistics, by arm, will be produced and box plots will be used to compare the distribution of the total TFV released.

11.3 Exploratory Acceptability Analyses

As an exploratory endpoint, the number and proportion of participants who reported a score of 9 or higher to question J2 ("Overall, how much do you like the ring?") will be tabulated by arm, along with 95% confidence intervals calculated using the Pearson-Clopper method. A second cut-off point will also be explored by tabulating the number and proportion of participants who reported a score of 5 or higher to question J2 by arm, along with the 95% confidence intervals.

A composite from answers to questions J1 ("Overall, how much do you like male condoms?") and J2 will be presented. Answers to both questions are recorded as Likert scales from 1 to 10. Additionally, the number and proportion of participants who reported a score as high or higher to question J2 than to question J1 will be tabulated by arm, with 95% confidence intervals.

For these endpoints, the proportions will be formally compared between the TFV IVR arm and the comparator placebo IVR arm using Fisher's exact test. A bar plot of scores reported for question J2, by arm, will be presented.

A bar plot of scores reported for question JJ4 "If the ring is found to be effective for HIV prevention, how likely would you be to use it in the future if it were available?" will be presented. The number and proportion of participants who reported a score of 9 or 10 to question JJ4 will be tabulated by arm, along with 95% confidence intervals calculated using the Pearson-Clopper method.

13. CHANGE HISTORY

Identify major changes. Only changes after version 1.0 approval need to be recorded.

Version		Affected Section(s)	Activity Description
Number	Effective Date
